11.3 Unanticipated Problems (UP)

The [Office for Human Research Protections](#) (OHRP) considers unanticipated problems involving risks to participants or others to include, in general, any incident, experience, or outcome that meets all of the following criteria:

- Unexpected in terms of nature, severity, or frequency given (a) the research procedures that are described in the protocol-related documents, such as the IRB-approved research protocol and informed consent document; and (b) the characteristics of the participant population being studied;
- Related or possibly related to participation in the research (“possibly related” means there is a reasonable possibility that the incident, experience, or outcome may have been caused by the procedures involved in the research); and
- Suggests that the research places participants or others at a greater risk of harm (including physical, psychological, economic, or social harm) than was previously known or recognized.

This study will use the OHRP definition of UP.

11.3.1 Unanticipated Problem Reporting

Incidents or events that meet the OHRP criteria for UPs require the creation and completion of an UP report form. It is the site investigator’s responsibility to report UPs to their IRB and to the DCC/study sponsor. The UP report will include the following information:

- Protocol identifying information: protocol title and number, PI’s name, and the IRB project number;
- A detailed description of the event, incident, experience, or outcome;
- An explanation of the basis for determining that the event, incident, experience, or outcome represents an UP;
- A description of any changes to the protocol or other corrective actions that have been taken or are proposed in response to the UP.

To satisfy the requirement for prompt reporting, UPs will be reported using the following timeline:

- UPs that are SAEs will be reported to the IRB, NIMH DSMB, and to the DCC/study sponsor within 3 business days of the investigator becoming aware of the event.

- Any other UP will be reported to the IRB, the NIMH DSMB, and to the DCC/study sponsor within 2 weeks of the investigator becoming aware of the problem.
- All UPs should be reported to appropriate institutional officials (as required by an institution's written reporting procedures), the supporting agency head (or designee), and OHRP within one month of the IRB's receipt of the report of the problem from the investigator.

12 DISCONTINUATION AND REPLACEMENT OF SUBJECTS

12.1 Early Discontinuation of Study Drug

A subject may be discontinued from study treatment at any time if the subject, the investigator feels that it is not in the subject's best interest to continue. The following is a list of possible reasons for study treatment discontinuation:

- Subject withdrawal of consent
- Subject is not compliant with study procedures
- Adverse event that in the opinion of the investigator would be in the best interest of the subject to discontinue study treatment
- Lost to follow-up
- Need for early termination of study
- Positive pregnancy test (females)

If a subject is withdrawn from treatment due to an adverse event, the subject will be discontinued from the study. The site PI will follow up with the subject until the abnormal parameter or symptom has resolved or stabilized. All subjects who discontinue study treatment should come in for an early discontinuation visit as soon as possible. All subjects are free to withdraw from participation at any time, for any reason, specified or unspecified, and without prejudice. Reasonable attempts will be made by the investigator to provide a reason for subject withdrawals. The reason for the subject's withdrawal from the study will be specified in the subject's source documents. Refer to section 10.6 "Study exit Visit (Visit 6 – Day 57) and early withdrawal" for early termination procedures.

12.2 Withdrawal of Subjects from the Study

A subject may be withdrawn from the study at any time if the subject or the investigator, feels that it is not in the subject's best interest to continue.

All subjects are free to withdraw from participation at any time, for any reason, specified or unspecified, and without prejudice.

Reasonable attempts will be made by the Investigator to provide a reason for subject withdrawals. The reason for the subject's withdrawal from the study will be specified in the subject's source documents. As noted above, subjects who discontinue study treatment early (i.e., they withdraw prior to Visit 6; Day 57) will have an early discontinuation visit. Please, refer to section 10.6 "Study exit Visit (Visit 6 – Day 57) and early withdrawal" for early termination procedures.

At the time of study discontinuation, the study team will discuss with the participants an appropriate venue of care. If appropriate and requested by the subject, reasonable efforts will be made by the study team to provide the participant information for consultation and appropriate transfer of care after study discontinuation.

12.3 Replacement of Subjects

Subjects randomized who withdraw or are discontinued from the study will not be replaced.

13 PROTOCOL DEVIATIONS

A Protocol Deviation (PD) is defined as any change, divergence, or departure from the IRB-approved study procedures in a research protocol.

In the present study, protocol deviations will be classified as either minor (non-serious) deviations or major (serious) deviations according to the definitions listed below:

Minor Protocol Deviations:

A minor protocol deviation occurs when accidental or unintentional changes are made to the research protocol (or non-compliance with the protocol) that does not increase risk or decrease benefit to subjects, or does not have a significant effect on the subject's rights, safety or welfare; and/or on the integrity of the primary outcome data. Deviations may result from the action of the subject, researcher, or research staff.

A minor protocol deviation may be due to the research subject's non-adherence, or an unintentional change to or non-compliance with the research protocol on the part of a researcher. Examples of a minor protocol deviation include:

- A rescheduled study visit or a study visit held out of window
- Failure to collect an ancillary self-report questionnaire

Major Protocol Deviations:

A major protocol deviation occurs when accidental or unintentional changes are made to (or non-compliance occurs with) the IRB approved protocol without prior sponsor and IRB approval that increases risk or decreases benefit to subjects, affects the subject's rights, eligibility, safety, or welfare, or the integrity of the primary outcome data. Examples of major protocol deviations include (but are not limited to):

- Failure to obtain valid informed consent
- Loss of laptop computer that contained identifiable, private information about subjects
- Accidental distribution of incorrect study medication or dose

Randomizing a subject who does not meet inclusion/exclusion criteria

Failure to comply with Good Clinical Practice (GCP) guidelines will also result in a major protocol deviation. The PI will determine if a major protocol deviation will result in withdrawal of a subject.

When a protocol deviation occurs, it will be discussed with the Site PI and a Protocol Deviation Form detailing the deviation will be generated. This form will be signed by the PI or delegated co-investigator. A copy of the form will be filed in the site's regulatory binder and in the Sponsor's files. A major protocol deviation that has the potential to impact participant safety will be reported to the DSMB as an immediately reportable event, within 3 business days of site awareness. Please refer to section 11.2.1 "AE/SAE Reporting Procedures" for more information.

14 DATA SAFETY MONITORING PLAN

14.1 Role of PIs in Safety Monitoring

The PIs will regularly monitor potential risks and procedures for protecting risk at each site. The PIs will have monthly teleconference meetings during which any serious adverse events (SAEs) or unexpected problems (UPs) will be discussed. The PIs will also meet in-person at a minimum of twice yearly to review all aspects of study progress and safety. Each PI is ultimately responsible for monitoring the data and safety at that site and will provide continuous, close monitoring of adverse events. The investigators and study coordinators will evaluate the progress of the study, including periodic assessments of data quality and timeliness, participant recruitment, accrual and retention, participant risk versus benefit, performance of the various sites, and other factors that can affect study outcome. They will also consider factors external to the study, such as scientific or therapeutic developments that may have an impact on the safety of the participants or the ethics of the study.

The overall study PI/Sponsor is responsible for AE reporting to the IRB, Data and Safety Monitoring Board (DSMB) (see below), and any other pertinent entities.

14.2 Data and Safety Monitoring Board (DSMB)

A Data and Safety Monitoring Board (DSMB) will be created by the NIMH as an independent body charged with ensuring that the safety of study subjects is protected and that the scientific goals of the study are being met. The DSMB conducts a review of all adverse events at least three times yearly, and reports their findings to the study PIs, who will inform their respective IRBs regarding the findings. The DSMB will be organized in compliance with the NIMH Charter, to ensure the safety of study participants and the integrity of the data collected in the projects. To achieve this goal, the DSMB will perform an ongoing evaluation of the overall clinical outcomes and the safety of patients participating in the clinical trial. The DSMB will also review any proposed amendments to the study protocol, perform expedited monitoring of immediately reportable serious adverse events, perform ongoing monitoring of all other AEs and SAEs, as well as drop-outs, determine whether study procedures should be changed or the study should be halted for reasons related to the safety of study subjects, and perform periodic review of the completeness and validity of data to be used for analysis of safety and efficacy. The DSMB will also ensure subject privacy and research data confidentiality. The DSMB will remain extrinsic to the study's infrastructure.

Please see Protocol Appendix for NIMH **DSMB Charter** for additional details.

15 CLINICAL MONITORING

Clinical site monitoring is conducted to ensure that the rights and well-being of human subjects are protected, that the reported trial data are accurate, complete, and verifiable, and that the conduct of the trial is in compliance with the currently approved protocol/amendment(s), with GCP, and with applicable regulatory requirement(s). See separate **clinical monitoring plan** (CMP) in **APPENDIX** for full details. The main features are below.

- Monitoring for this study will be performed by NIMH Clinical Trials Operations and Biostatistics Branch (CTOBB) monitors.
 - Monitoring will be conducted on-site, throughout the study, and involve targeted data verification of key data variables
 - The site PI will be provided copies of monitoring reports within 10 days of visit, and will be provided to the NIMH DSMB liaison within 30 days of the visit.
 - Details of clinical site monitoring are documented in the CMP. The CMP describes who will conduct the monitoring, at what frequency monitoring will be done, at what level of detail monitoring will be performed, and the distribution of monitoring reports.
 - The site will perform internal quality management of study conduct, data collection, documentation and completion. An individualized quality management plan will be developed to describe the site's quality management.

16 STATISTICAL METHODS AND CONSIDERATIONS

The Statistical Analysis Plan (SAP) will contain any modification to the analysis plan described below, and in the case of a discrepancy between the protocol and the SAP, all analyses will be performed according to the SAP. Any modifications will be made prior to the unblinding of study data.

16.1 Data set analyzed

Data will be analyzed on an intent-to-treat basis, i.e., patients will be analyzed according to the treatment assigned by randomization regardless of the treatment actually received. Patients missing the follow up fMRI will be excluded from the primary outcome analysis. As it is impossible to test the missingness mechanism and data may not be missing completely at random, a secondary sensitivity analysis will be conducted using multiple imputation for the primary endpoint to investigate possible violations of the missing at random assumption. Extreme case imputation, whereby the lowest and highest overall observed values for the primary endpoint are imputed for any missing value, will also be used to assess the robustness of the primary endpoint analysis.

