1.2.2 Randomization and masking

Patients will be randomized in a 1:1 allocation to ezogabine or placebo. Randomization will be stratified by center balanced by randomly permuted blocks, and treatment code will be allocated through the interactive web response system (IWRS). Randomization will take place only after it has been determined that all study eligibility criteria have been met and the baseline fMRI scan has been obtained.

This is a double-blind, placebo-controlled trial. Site personnel and patients will be blinded to treatment assignment throughout the trial.

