2. STUDY POPULATIONS

Intent-to-Treat (ITT) Population

The ITT population is defined as all randomized subjects, regardless of when they withdrew from the study or received the assigned treatment. The ITT population will be used to present all data (including the primary endpoint) by randomized treatment group. Subjects will be analyzed according to the treatment to which they were randomized, regardless of the treatment they actually received.

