5. STATISTICAL METHODOLOGY

5.1 Statistical Methods

All data will be presented by treatment group as well as for the whole sample.

For all baseline, demographic and efficacy variables, data will be summarized and analyzed by randomized treatment group as per ITT.

In summary tables of normally distributed continuous variables, the following descriptive statistics will be used: minimum and maximum, mean, and standard deviation (SD). In summary tables of non-normally distributed variables data will be presented using the minimum, maximum, median and lower and upper quartiles.

In summary tables of categorical variables, counts and percentages will be used. The denominator for each percentage will be the number of patients within the randomization group unless otherwise specified.

Rates of events will be calculated as the ratio of the total number of events recorded divided by the total patient-time in study (months or days). Total patient-time will be

calculated by summing the time (in days) that patients were at risk for a specific event from the time they were randomized in the study until study exit. Rates and 95% confidence intervals will be reported.

For any variable measured at multiple points in time, change from baseline will be calculated as the difference between the value of the variable at a specific point in time (e.g. 5 weeks) minus the baseline value.

Relative change from baseline will be calculated as the value of a parameter at a specific point in time minus the baseline value of the parameter divided by the baseline value of the parameter.

Percent change will be calculated as the relative change multiplied by 100.

Hypothesis testing will be conducted at the 0.05 two-sided significance level for the primary endpoint. No formal hypothesis tests will be conducted for the secondary endpoints, rather, we will calculate estimates and 95% confidence intervals by group.

P-values will be rounded to three decimal places. P-values less than 0.001 will be reported as <0.001 in tables. P-values greater than 0.999 will be reported as >0.999.

Should any of the statistical methods proposed prove unsuitable during data analysis, more appropriate methods will be used. These include data transformation (for example to a logarithmic scale) to satisfy model assumptions such as normally distributed residuals with constant variance, or the application of non-parametric techniques.

Additional ad-hoc analyses may be conducted as deemed appropriate.

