5.2.1 Missing values for the primary outcome

Missing outcome values for primary endpoint analysis will not be imputed. For the primary endpoint, missing data can be the result of patient refusal, missed visit, or study dropout (withdrawal, lost to follow-up). Missing data due to patient refusal or missed visits are assumed to be missing at random (MAR). Study dropout is also assumed to be MAR.

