5.4 Efficacy Analysis

5.4.1 Analysis of Primary Endpoint and Determination of Sample Size

The primary endpoint is the change in activation of the bilateral VS, a region of the rewards circuit in the brain, at 5 weeks from randomization. Activation will be measured by fMRI, and beta weights for each subject will be calculated to create a contrast between gain and neutral cues to model reward anticipation as described in the Neuroimaging Methods section of the protocol. To calculate the beta weight for the bilateral VS, the beta weights for the right and left VS will be averaged.

A linear mixed effects model with a single random intercept term will be used to assess the change in activation of the bilateral VS by treatment group. A sample size of 48 provides 85% power to detect a difference in means between groups of 0.8 standard deviations assuming a correlation of 0.6 between a pair of measurements made on the same subject using a two-sided 0.05 significance level test.

Although randomization is stratified by site, the primary endpoint analysis will be of the pooled dataset; secondary analyses will provide site-specific estimates.

No adjustment to the primary analysis will be made for baseline measures that are found to be imbalanced but, if applicable, secondary sensitivity analyses may adjust for any factors that are imbalanced at a significance level below $p = 0.05$. (Altman, 1985) (Peter Peduzzi, 2002) (Senn, 1989) (Senn, Testing for baseline balance in clinical trials, 1993)

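### Protocol 16.1 excludes patients without a follow-up scan, and the SAP does not clearly keep them in the primary model, although it assumes MAR in all randomised patients

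*Protocol*

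**What the plan says.** Protocol 16.1 describes the analysis as intent-to-treat and then adds: "Patients missing the follow up fMRI will be excluded from the primary outcome analysis". SAP 2 defines ITT as everyone randomised and continues: "The ITT population will be used to present all data (including the primary endpoint) by randomized treatment group". SAP 5.2.1 does not impute missing outcomes in the primary analysis. It treats refusal and missed visits as missing at random and adds: "Study dropout is also assumed to be MAR".

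The model in SAP 5.4.1 is: "A linear mixed effects model with a single random intercept term will be used to assess the change in activation". The power statement beside it is framed "assuming a correlation of 0.6 between a pair of measurements made on the same subject". SAP 5.4.1 does not say which rows enter the model or which coefficient is the treatment effect.

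Four other provisions bear on the point:
- Protocol 16 gives the SAP precedence in any discrepancy and requires changes to be made before unblinding.
- SAP 1.2.2 places randomisation after the baseline scan, so a patient with no V5 scan should still have a V0 value.
- SAP 3.1 makes the primary endpoint the only go/no-go criterion.
- Protocol 12.3 does not replace withdrawals.

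**The concern.** In a two-visit mixed model, a patient with only a V0 scan is not empty. That scan helps to estimate the arm's baseline mean, and through the within-subject correlation it corrects the V5 mean for who was lost. The SAP's MAR assumption supports a likelihood fit that keeps those scans. It does not in general support an analysis that deletes them.

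The protocol contains an explicit deletion rule, and the SAP contains no equally explicit retention rule. Not imputing is compatible with both. An analyst could therefore read the protocol sentence as filling a gap in the SAP rather than as contradicting it. At stake is whether the analysis behind the go/no-go decision is valid under the assumption the SAP states for it. SAP 5.2.3 treats the matter as open, since it plans to check whether patients without a V5 scan differ in baseline reward-circuit activation and in treatment group.

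**Working it through.** **Inputs from the documents.** "A sample size of 48 provides 85% power to detect a difference in means between groups of 0.8 standard deviations" (SAP 5.4.1), with correlation 0.6. "Patients will be randomized in a 1:1 allocation to ezogabine or placebo" (SAP 1.2.2), so 24 per arm. "Hypothesis testing will be conducted at the 0.05 two-sided significance level for the primary endpoint" (SAP 5.1). No missing-scan rate is given, so every loss pattern below is an assumption.

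**Step 1: reproduce the stated power.** In units of the single-visit SD, the SD of a change score is √(2 × (1 − 0.6)) = 0.894. The standard error of the difference is 0.894 × √(2/24) = 0.258, and 0.80/0.258 = 3.10. A noncentral t test on 46 df gives 85.8%, which agrees with the stated 85%. The plan's figure therefore corresponds to a full set of change scores. With 19 completers per arm (about 20% loss) the same formula gives 76.5%.

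**Step 2: what the exclusion does.** With both scans present for every patient analysed, the treatment-by-visit estimate equals the difference in mean change. For a patient whose baseline is x (in SD from the common mean), expected change is the treatment effect minus (1 − 0.6)x. Let m_E and m_P be the completers' mean baselines on ezogabine and placebo. Then

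expected completer estimate = 0.80 − 0.4 × (m_E − m_P).

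Keeping the V0-only rows adds back, in each arm, 0.4 × (completers' baseline mean − all patients' baseline mean), which removes the second term. Dependence of loss on baseline is therefore not enough to cause bias, because if it is the same in both arms then m_E = m_P and it cancels. The sign also depends on who is lost: losing low-baseline patients on ezogabine biases the estimate down, and losing high-baseline patients biases it up.

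**Step 3: an adverse case.** Assume logit P(loss) = −1.6 − 1.5 × baseline on ezogabine and 10% random loss on placebo. Ezogabine loss is then 24%, with baseline mean −0.84 among those lost and +0.27 among completers (check: 0.24 × −0.84 + 0.76 × 0.27 ≈ 0). The expected completer estimate is 0.80 − 0.4 × 0.27 = 0.69.

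**Step 4: milder cases, still 24% versus 10% loss.** With slope 1.5 in both arms the estimate is about 0.74, an arm difference in completer baselines of (0.80 − 0.74)/0.4 = 0.15 SD. With slope 0.5 on ezogabine only it is about 0.75, a difference of about 0.125 SD.

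**Step 5: simulation.** Bivariate normal V0/V5 data (SD 1, correlation 0.6, 0.8 SD shift) were analysed with a random-intercept REML model, once on completers and once on all rows. Runs used 1,500 to 4,000 trials per scenario, with a standard error of at most about 1 percentage point.

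| Assumed loss | Estimate, completers | Estimate, all scans | Power, completers | Power, all scans |
|---|---|---|---|---|
| 20% random, both arms | 0.80 | 0.80 | 76-77% | 79% |
| 20%, same baseline dependence in both arms (slope 1) | 0.80 | 0.80 | 77% | 77% |
| 24% vs 10%, milder arm-specific patterns | about 0.75 | 0.80 | up to 74% | about 80% |
| 24% vs 10%, steep slope on ezogabine only | 0.69 | 0.80 | about 66% | about 80% |
| 20%, opposite slopes by arm (slope 1) | 0.66 | 0.80 | 61% | 78% |

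The two fits fall on different sides of p < 0.05 in about 5% of trials under 20% random loss and about 5-7% under heavier loss with the same baseline dependence in both arms. The share is 12-15% in the steep case and 17% with opposite slopes.

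**The case against.** The strongest reply is that Protocol 16 already settles the matter. If SAP 2 conflicts with Protocol 16.1, the SAP wins and there is one population. A reader might infer that the sponsor may run the test on either population and choose, and the documents do not support that. The SAP's own terms also point to retention. A random intercept cannot be separated from residual error with one change score per patient, so the response is most naturally the V0/V5 pair. With ITT, MAR, no imputation and a SAS mixed model, V0-only patients would stay in by default. If the response were the change score, the two data sets would give identical results. All of this stands, but it is inference from defaults set against an explicit deletion rule.

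The planned safeguards also count. Protocol 10.6 obtains a scan at early withdrawal, which reduces the number of V0-only patients. Both documents plan multiple imputation and lowest- and highest-value imputation. If the imputation model includes baseline and arm, it targets the same estimate as the all-scans model. These are sensitivity analyses, however, and do not say which result is primary.

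Finally, nothing in the documents shows that loss will be selective by arm. Missing scans are plausible, since the pilot in Protocol 1.2 had both scans for 6 of 9 patients. Loss differing by arm is also plausible given the listed side effects and the early exit for persistent intolerance (Protocol 8.4.1). The link to baseline activation is assumed.

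**Conclusion.** The point holds as a gap in specification. Protocol 16.1 states an exclusion that is not valid in general under the MAR assumption of SAP 5.2.1, and the SAP does not displace it in words.

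The size depends on the assumed loss. With random loss, or loss tied to baseline identically in both arms, there is no bias and the power cost is at most 2 to 3 points. With 24% versus 10% loss and arm-specific dependence on baseline, the completer estimate falls by about 0.05 to 0.11 SD and power is 66-74% instead of about 80%. Opposite slopes by arm, a deliberately extreme case, lower the estimate by 0.14 SD.

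Two stronger inferences are not supported. First, loss related to baseline does not by itself bias the completer analysis; the relation must leave different completer baselines in the two arms. Second, disagreement at p < 0.05 is not the same as opposite go/no-go decisions. SAP 3.1 names the endpoint but no p-value threshold, and Protocol 2.1 speaks of both significance and effect size.

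The figures assume normal data, equal variances at both visits, the plan's correlation of 0.6, and MAR given baseline and arm. Keeping V0-only scans does not protect against loss that depends on the unseen V5 value.

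**What to change.** Delete the exclusion sentence in Protocol 16.1. In SAP 5.4.1, state that the primary model is fitted by REML to every available V0 and V5 ventral striatum value in the ITT population, including patients with only a V0 scan, and that the treatment-by-visit term is the treatment effect. Report the completers-only result as a sensitivity analysis beside those in SAP 5.2.3.

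The cost is a few sentences before unblinding. No new data are needed, and the SAS mixed procedure already accepts patients with one scan. The gain is small unless loss differs by arm, but the change makes the primary analysis consistent with the SAP's own missing-data assumption.
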